10.1.2 Power estimations

We expect to have the following statistical power for the secondary outcomes based on 2 x 777 participants, a type 1 error level of 1% and a relative risk reduction of 15% in the experimental vs control group:

- 50% power for the number of participants with one or more SAEs (control event rate 25%)
- 10% power for the number of participants with one or more SARs (control event rate 5%)
- 80% power for the mortality at 1-year (control event rate 55%).

The estimates of control event rates originate in data of previous septic shock trials [2, 3]. We expect the following outcomes to be highly skewed (non-normally distribution): Days alive without life support and out of hospital at day 90 and HRQoL and cognitive function at 1-year. The power estimations for these are, therefore, somewhat uncertain why we refrain from making these estimates.

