Restricting fluid therapy may be beneficial in reducing venous back-pressure and organ oedema, thereby improving organ function including that of the lungs, gut and kidneys [26, 27]. On the other hand, fluid restriction may also compromise peripheral and/or organ perfusion through reduced cardiac output and thereby reduced microcirculation from the arterial side [28]. Thus, the physiological data support the clinical equipoise and the need for large trials on IV fluid volumes in patients with septic shock.

Following these notions, a recent consensus statement from key opinion leaders within the field of intensive care medicine gave the highest priority to trials on restrictive vs. liberal fluid therapy when prioritizing the topics that need testing in patients with septic shock [29].

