10.1 Sample size and power

10.1.1 Sample size estimation

By enrolling 1554 (2 x 777) participants, we can show a 15% relative risk reduction (7% absolute) in the restrictive group from an estimated 45% 90-day mortality in the standard care group (data from our previous CLASSIC pilot, TRISS and 6S trials [2, 3, 5], systematic reviews [23, 44] and a recent large cohort study [4]) at type 1 and 2 error levels of 5% and 20% (power=80%), respectively.

The CLASSIC trial protocol Page 31/82

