10.2 Statistical methods

The analyses will be done in the intention-to-treat (ITT) population defined as all randomised participants for whom there is consent for the use of data. We will perform the primary analyses adjusted for the stratification variables [45] and challenge the primary result in analyses adjusted for important baseline risk factors (co-morbidities, higher SMS score, and focus of infection (other foci vs. urinary tract infection)[43, 46] and use of corticosteroids, which may reduce the time in ICU and thus the time exposed to the protocol [47]) and analyses of subgroups (Table 2) and the per-protocol population being the ITT population except those having one or more major protocol violations as defined below (Table 3). If there is more than 5% missing data for outcomes and/or covariates, we will impute the missing data using multiple imputations as described below (10.2.4).

All analyses will be 2-tailed and we will use Fisher's exact test for unadjusted comparisons of dichotomized outcomes (mortality at 90-days and 1-year, SAEs and SARs) and logistic regressions for adjusted analyses of these outcomes. The remaining secondary outcomes are continuous measures; we expect that these are highly skewed (non-normally distribution), because of inflation of specific values such as zero for days alive outside hospital for all patients who die while at the ICU. We will use statistical methods that can accommodate this type of data; the precise models will be specified in the detailed statistical plan.

Several of the secondary outcome measures are composite; we will also analyse each component of these outcomes as recommended [42]; the precise models will be specified in the detailed statistical plan.

Table 2. Heterogeneity of the intervention effects on the primary outcome will be analysed in the following subgroups based on baseline characteristics

Subgroup	Definition	Expected direction of	Statistical test
		the interaction	
Participants who are mechanically ventilated	Invasive mechanically ventilated (yes/no)	Larger effect of fluid restriction in mechanically ventilated participants	Test of interaction in the adjusted analysis described above; P- value 0.01

The CLASSIC trial protocol Page 32/82

Participants with	KDIGO (creatinine)	Larger effect of fluid	Test of interaction in
severe acute kidney	criteria of 2 or above	restriction in acute	the adjusted analysis
injury	[41] (yes/no)	kidney injury	described above; P-
			value 0.01

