Generalised linear model or nonparametric test stratified for site in the ITT population For the generalised linear model we will initially use Poisson distribution, alternatively negative binomial.¹⁸ If the assumptions for Poisson distribution or negative binomial distribution are not met, data will be analysed using the nonparametric Van Elteren test adjusted for site, but no other variables.¹⁹

The following secondary outcome measures are composite; SAEs, SARs, days alive at day 90 without life support. We will report each component of these outcomes in an appendix to the primary publication without P-values due to the lack of adjustment for multiple comparisons. We will report absolute and relative risk ratios with 99% CIs for dichotomous secondary outcomes. For continuous secondary outcomes we will report mean differences with 99% CIs if they are normally distributed and medians with 99% percentile-based bootstrapped CIs for non-normally distributed continuous secondary outcomes (P-value 0.01) due to the multiplicity of these. A detailed definition of the level of significance for the secondary outcomes is available in the supplement to the published statistical analysis plan. ¹

Sample size

Primary outcome

We plan to enrol 1554 (2 x 777) patients to be able to show a 15% relative risk-reduction (RRR) (7% absolute) in the restrictive group on the primary outcome from an estimated 45% 90-day mortality in the standard care group at type 1 and 2 error levels of 5% and 20% respectively, corresponding to a number needed to treat (NNT) of 14 or less. The anticipated relative risk reduction of mortality and the estimated mortality in the control group is based on data from previous RCTs and systematic reviews.^{20–24}

Trial sequential analysis of existing trials (n=8) have shown that less than 15% of the required information size of 3956 patients to detect or reject a 15% RRR in all-cause mortality with lower versus higher fluid volumes has been reached.²⁵

Secondary outcomes

We expect to have the following statistical power for the secondary outcomes based on 2 x 777 participants, a type 1 error level of 1% and a RRR of 15% in the fluid restriction group versus standard care group:

- 50% power for the number of participants with one or more SAEs (control event rate 25% ^{21,22})
- 10% power for the number of participants with one or more SARs (control event rate 5%^{21,22})

- 80% power for the mortality at 1-year (control event rate 55%^{21,22})

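### The stated powers for SAEs (50%) and SARs (10%) do not follow from their stated inputs, which give about 21% and 3%

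*Protocol*

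**What the plan says.** Protocol 10.1.2 sets out the power for three binary secondary outcomes, based on 2 x 777 participants, "a type 1 error level of 1% and a relative risk reduction of 15"%. It then states:

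- SAEs: "50% power for the number of participants with one or more SAEs (control event rate 25"%)
- SARs: "10% power for the number of participants with one or more SARs (control event rate 5"%)
- 1-year mortality: 80% power at a control rate of 55%

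The SAP (Sample size, Secondary outcomes) repeats the inputs and the results: "50% power for the number of participants with one or more SAEs" and "10% power for the number of participants with one or more SARs", with the same control rates.

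The remaining input is the sidedness. Protocol 10.2 says "All analyses will be 2-tailed", and the SAP specifies two-tailed logistic regression for these outcomes. The 1% level is deliberate. Protocol 10.2.1 pairs it with 99% confidence intervals, and section 1 of the SAP appendix chooses it as a value between 0.0125 and 0.0071. The SAP's summary of changes does not revise any of the power figures.

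**The concern.** Nothing has to be assumed to check these figures, because sample size, error level, sidedness, effect and control rates are all given. A fall from 25% to 21.25% is an absolute difference of 3.75 percentage points. That is little more than half of the 7-point difference for which the trial has 80% power, and it is tested at a stricter level. A power of 50% is implausible on those terms.

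The SAE composite is the outcome at stake. It combines ischaemic events with severe acute kidney injury, and Protocol 1.3 notes that "fluid restriction may also compromise peripheral and/or organ perfusion". The same paragraph also allows that restriction may improve organ function, so an effect in either direction is of interest. Anyone reading a non-significant SAE result against the plan would credit the trial with much more ability to detect a 15% change than it has.

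**Working it through.** **Formula.** For n per group, control rate pc, experimental rate pt and mean rate p̄ = (pc + pt)/2:

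- SE0 = √[2 p̄(1 − p̄)/n]
- SE1 = √[(pc(1 − pc) + pt(1 − pt))/n]
- power = Φ[(|pc − pt| − z·SE0)/SE1], where z is 1.960 for two-sided 5% and 2.576 for two-sided 1%

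**Step 1: reproduce the primary calculation.** Protocol 10.1.1 says "we can show a 15% relative risk reduction (7% absolute) in the restrictive group" from 45%, at 5% type 1 error and 80% power. With 45% vs 38%, SE0 = 0.02500 and SE1 = 0.02494. Then (0.07 − 1.960 × 0.02500)/0.02494 = 0.842, and power is **80.0%**. The formula matches the plan. The rounded 7 points correspond to a relative reduction of 7/45 = 15.6%; at exactly 15% (38.25%) the power is 77.1%.

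**Step 2: apply it to the secondary outcomes.** n = 777, two-sided 1%, pt = 0.85 × pc.

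| Outcome | pc vs pt | SE0 | SE1 | (difference − 2.576·SE0)/SE1 | Power | Stated |
|---|---|---|---|---|---|---|
| SAE | 25% vs 21.25% | 0.02139 | 0.02137 | (0.0375 − 0.0551)/0.02137 = −0.824 | **20.5%** | 50% |
| SAR | 5% vs 4.25% | 0.01066 | 0.01065 | (0.0075 − 0.0274)/0.01065 = −1.872 | **3.1%** | 10% |
| 1-year mortality | 55% vs 46.75% | 0.02536 | 0.02528 | (0.0825 − 0.0653)/0.02528 = 0.679 | **75.2%** | 80% |

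Fisher's exact test, which Protocol 10.2 names for unadjusted comparisons, gives lower values: 18.9%, 2.4% and 74.0%. For a 15% relative increase in SAEs (25% vs 28.75%), the normal approximation gives 18.2%.

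**Step 3: look for a reading that recovers the stated figures.**

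| Change to the inputs | SAE | SAR | 1-year mortality |
|---|---|---|---|
| 15.6% relative reduction, two-sided 1% | 22.5% | 3.3% | 78.8% |
| Two-sided 0.0125 | 22.8% | 3.6% | 77.6% |
| One-sided 1% | 28.3% | 5.2% | 82.4% |
| Two-sided 5% | 41.8% | 10.4% | 90.3% |
| One-sided 5% | 54.3% | 17.3% | 94.7% |
| 1,554 per group, two-sided 1% | 46.2% | 5.7% | 97.9% |
| **Stated** | **50%** | **10%** | **80%** |

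The SAR column counts rejections in the expected direction only. Counting both tails moves the two-sided 5% entry to 10.8% and leaves the 1% result at 3.1%. No row fits all three outcomes. Solving for the two-sided level that yields each stated power at a 15% reduction gives 0.080 (SAE), 0.045 (SAR) and 0.016 (1-year mortality), so no single error level lies behind the set.

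**Step 4: what the stated powers would require at two-sided 1%.**

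- 50% for SAEs: about 1,678 per group, or a relative reduction of about 22%, or a control rate of about 43%.
- 10% for SARs: about 2,630 per group, or a relative reduction of about 27%.
- 80% for 1-year mortality: a relative reduction of about 15.7%.

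**The case against.** The strongest reply is that little depends on these numbers. The sample size is fixed by 90-day mortality, the 1% level comes from a multiplicity argument, and results will be reported with 99% confidence intervals, which show directly how precise a null SAE result is. A stated power of 50% already warned that the outcome was underpowered, and for SARs 10% and 3% carry nearly the same message. The SAP dates the final analyses to March 2022, so a correction now serves the record. All of this stands, and it limits the consequence. It does not make the figures correct.

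A second point is that the check in step 1 succeeds with a 15.6% reduction while step 2 uses exactly 15%. That is fair, and it plausibly explains the 1-year mortality gap (78.8% against 80%). It moves SAEs by only two points, to 22.5%.

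Third, two variants do come closer for SAEs: one-sided 5% (54.3%) and 1,554 per group (46.2%, or 49.9% with the 15.6% reduction). Both contradict stated inputs, and neither fits the other outcomes.

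Finally, the planned analysis adjusts for site and cancer status, whereas the formula is unadjusted. To bring SAEs to 50%, adjustment would have to be worth 1,678/777 = 2.2 times the sample size. Nothing in the documents suggests a gain of that order.

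**Conclusion.** The concern holds. On the plan's own inputs, SAE power is about 21%, so the stated 50% is overstated about 2.4-fold (50/20.5). SAR power is about 3% against 10%. The 1-year mortality figure is about 75% at exactly 15% and about 79% at 15.6%, so its gap from 80% is minor.

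This rests on the stated control rates, equal groups of 777 with complete data, a two-sided 1% test and an unadjusted comparison of proportions. Exact testing lowers the SAE and SAR figures slightly further. The SAE figure is the one that could mislead. It is worth correcting because it is large, appears in both documents and concerns the main safety composite, but it does not affect the trial's size or its analyses.

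**What to change.** In Protocol 10.1.2 and in the SAP's sample-size section, restate the powers with one effect size throughout:

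- at exactly 15% relative reduction: about 21% (SAEs), 3% (SARs) and 75% (1-year mortality); or
- if the 15.6% behind the 7-point primary difference is meant, say so and give about 22%, 3% and 79%.

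Keeping the stated powers and quoting the reductions they correspond to (about 22%, 27% and 16%) would also be arithmetically correct. It is the weaker choice, because it replaces one common effect with three values chosen to preserve the old figures.

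The cost is wording in two places and less favourable stated powers. Sample size, analyses, the 1% threshold and the 99% intervals stay as they are.

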10.2 Statistical methods

The analyses will be done in the intention-to-treat (ITT) population defined as all randomised participants for whom there is consent for the use of data. We will perform the primary analyses adjusted for the stratification variables [45] and challenge the primary result in analyses adjusted for important baseline risk factors (co-morbidities, higher SMS score, and focus of infection (other foci vs. urinary tract infection)[43, 46] and use of corticosteroids, which may reduce the time in ICU and thus the time exposed to the protocol [47]) and analyses of subgroups (Table 2) and the per-protocol population being the ITT population except those having one or more major protocol violations as defined below (Table 3). If there is more than 5% missing data for outcomes and/or covariates, we will impute the missing data using multiple imputations as described below (10.2.4).

All analyses will be 2-tailed and we will use Fisher's exact test for unadjusted comparisons of dichotomized outcomes (mortality at 90-days and 1-year, SAEs and SARs) and logistic regressions for adjusted analyses of these outcomes. The remaining secondary outcomes are continuous measures; we expect that these are highly skewed (non-normally distribution), because of inflation of specific values such as zero for days alive outside hospital for all patients who die while at the ICU. We will use statistical methods that can accommodate this type of data; the precise models will be specified in the detailed statistical plan.

Several of the secondary outcome measures are composite; we will also analyse each component of these outcomes as recommended [42]; the precise models will be specified in the detailed statistical plan.

Table 2. Heterogeneity of the intervention effects on the primary outcome will be analysed in the following subgroups based on baseline characteristics

Subgroup	Definition	Expected direction of	Statistical test
		the interaction	
Participants who are mechanically ventilated	Invasive mechanically ventilated (yes/no)	Larger effect of fluid restriction in mechanically ventilated participants	Test of interaction in the adjusted analysis described above; P- value 0.01

The CLASSIC trial protocol Page 32/82

Participants with	KDIGO (creatinine)	Larger effect of fluid	Test of interaction in
severe acute kidney	criteria of 2 or above	restriction in acute	the adjusted analysis
injury	[41] (yes/no)	kidney injury	described above; P-
			value 0.01
Participants with	Plasma lactate level	Larger effect of fluid	Test of interaction in
severe metabolic	above 4 mmol/l	restriction in severe	the adjusted analysis
failure	(yes/no)	metabolic failure	described above; P-
			value 0.01
Participant weight	Weight tertiles as	Larger effect of fluid	Test of interaction in
	observed in the 6S and	restriction with lower	the adjusted analysis
	TRISS trial cohorts	weight	described above; P-
	combined [2, 3]		value 0.01
IV fluid volume given	30 ml/kg or more	Larger effect of fluid	Test of interaction in
prior to randomisation	given (yes/no)	restriction with less	the adjusted analysis
		fluid given	described above; P-
			value 0.01

Table 3. The definitions of major protocol violations, the exclusion of which will form the perprotocol population

Intervention group	Major protocol violation definition
IV fluid restriction	IV fluids given without one of the extenuating
	circumstances occurring
Standard of care	No IV fluids given

10.2.1 Significance

We will present the results as adjusted absolute and relative risk differences, computed using glm-models with appropriate link functions and binomial error-distribution, with confidence intervals (CI) using 95% CIs for the analyses of primary outcome (P-value 0.05) and 99% CIs for those of the secondary outcomes (P-value 0.01) due the multiplicity of these.

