10.2.2 Interim analysis

We will conduct three interim-analyses; one when 10% of participants have been followed for 30-days, one when 30% of participants have been followed for 30-days and one when 50% of participants have been followed for 90-days. The Data Monitoring and Safety Committee (DMSC) will analyse only the fluid volumes and protocol violations in the two intervention groups in the two interim analyses to ensure that separation is occurring. At the third interim analysis they will assess fluid volumes, protocol violations, the 90-day mortality and the rates of SAEs and SARs in the ICU in the two intervention groups as described in the charter (Appendix 4). The DMSC will submit their recommendations to the Management Committee, which make the final decision regarding the continuing, pausing or stopping of the trial as described in the DMSC charter.

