10.2.3 Early stopping criteria

The trial will not be stopped unless the cumulative Z-value for effect size supersedes the Lan DeMets group sequential monitoring boundary corresponding to a P-value for effect of less than 0.005

The CLASSIC trial protocol Page 33/82

(approximately). The trial will not be stopped for futility as an intervention effect less than a 15% relative risk reduction may be clinically relevant. However, the DMSC can recommend pausing or stopping the trial if continued conduct of the trial clearly compromises participant safety.

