14.4 Appendix 4. Charter for the independent data monitoring and safety committee

Introduction

The DMSC will constitute its own plan of monitoring and meetings. However, this charter will define the minimum of obligations and primary responsibilities of the DMSC as perceived of the Management Committee (MC), its relationship with other trial components, its membership, and the purpose and timing of its meetings. The charter will also outline the procedures for ensuring confidentiality and proper communication, the statistical monitoring guidelines to be implemented by the DMSC, and an outline of the content of the open and closed reports which will be provided to the DMSC.

Primary responsibilities of the DMSC

The DMSC will be responsible for safeguarding the interests of trial participants, assessing the safety and efficacy of the interventions during the trial, and for monitoring the overall conduct of the clinical trial. The DMSC will provide recommendations about stopping or continuing the trial to the MC of the CLASSIC trial. To contribute to enhancing the integrity of the trial, the DMSC may also formulate recommendations relating to the selection/recruitment/retention of participants, their management, improving adherence to protocol-specified regimens and retention of participants, and the procedures for data management and quality control.

The DMSC will be advisory to the MC. The MC will be responsible for promptly reviewing the DMSC recommendations, to decide whether to continue or terminate the trial, and to determine whether amendments to the protocol or changes in trial conduct are required.

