The DMSC may meet physically or by phone at their own discretion in order to evaluate the planned interim analyses of the CLASSIC trial. The interim analyses will be performed by an independent statistician selected by the members of the DMSC, NAME (pending) from the Dept. of Biostatistics, University of Copenhagen. The DMSC may additionally meet whenever they decide or contact each other by telephone or e-mail to discuss the safety for trial participants. The sponsor has the responsibility to report the overall number of SARs yearly to the DMSC. The DMSC can, at any time during the trial, request the distribution of events, including outcome measures and SARs according to intervention groups. Further, the DMSC can request unmasking of the interventions if suggested by the data, see section on 'closed sessions'. The recommendations of the DMSC regarding stopping, continuing or changing the design of the trial should be communicated without delay to the MC of the CLASSIC trial. As fast as possible, and no later than 48 hours, the MC has the responsibility to inform all investigators of the trial and all the sites including patients in the trial, about the recommendation of the DMSC and the MC decision hereof.

Members of the DMSC

The DMSC is an independent multidisciplinary group consisting of clinicians and a biostatistician that, collectively, has experience in the management of ICU patients and in the conduct, monitoring and analysis of randomized clinical trials.

The CLASSIC trial protocol Page 54/82

DMSC Clinician Pending

DMSC Trialist Pending

DMSC Biostatistician

Pending. Dept. of Biostatistics, University of Copenhagen

Conflicts of interest

DSMC members will fill in and sign a declaration of conflicts of interests (Appendix 10). DMSC membership has been restricted to individuals free of conflicts of interest. The source of these conflicts may be financial, scientific, or regulatory in nature. Thus, neither trial investigators nor individuals employed by the sponsor, nor individuals who might have regulatory responsibilities for the trial products, are members of the DMSC. The DMSC members do not own stock in the companies having products being evaluated by the CLASSIC trial.

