Sensitivity analyses:

A two-tailed logistic regression analysis adjusted for the stratification variables, the SMS-ICU¹⁴ focus of infection (other foci versus urinary tract infection)^{14,16} and use of corticosteroids¹⁷
 A two-tailed logistic regression analysis in the per-protocol population adjusted for the stratification variables

4. Two-tailed logistic regression analyses in the pre-planned subgroups adjusted for the stratification variables

We will report absolute and relative risk ratios with 95% CIs for the primary analysis of the primary outcome (analysis 1) (P-value <0.05), computed using glm-models with appropriate link functions and binomial error-distribution. Further, we will report the crude event rates in each group and a Kaplan-Meier survival curve for the crude data of the primary outcome.

Secondary outcomes

Dichotomous secondary outcomes will be analysed in the same way as the primary analysis for the primary outcome, i.e.:

• SAEs

Two-tailed logistic regression adjusted for the stratification variables in the ITT population

- SARs
 Two-tailed logistic regression adjusted for the stratification variables in the ITT population
- 1-year mortality

Two-tailed logistic regression adjusted for the stratification variables in the ITT population

A Kaplan-Meier survival curve will be reported for the crude data for secondary outcome 1-year mortality.

The remaining secondary outcomes are continuous measures which we expect to be skewed (nonnormally distributed), because of inflation of specific values such as zero for 'days alive outside hospital' for all patients who die while in the ICU. The outcome measures will be analysed as follows:

- Days alive at day 90 without life support
 Generalised linear model or nonparametric test stratified for site in the ITT population
- Days alive and out of hospital at day 90
 Generalised linear model or nonparametric test stratified for site in the ITT population
- HRQoL 1-year after randomisation⁸
 Generalised linear model or nonparametric test stratified for site in the ITT population
- Cognitive function 1-year after randomisation⁹

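### The final mortality test keeps the full two-sided 0.05 after an alpha-spending look at 50%, so overall type 1 error is about 5.1% to 5.2% if that boundary is acted on (minor)

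*Protocol*

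**What the plan says.** **Error level.** Protocol 10.1.1 sizes the trial "at type 1 and 2 error levels of 5% and 20% (power=80%), respectively", and the SAP sample-size section repeats both levels. Protocol 10.2 adds "All analyses will be 2-tailed".

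**Interim looks.** Three are planned. The first two cover only fluid volumes and protocol violations. Mortality enters once, when half of the participants have 90-day follow-up: "At the third interim analysis they will assess fluid volumes, protocol violations, the 90-day mortality" (Protocol 10.2.2).

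**Boundary.** Protocol 10.2.3 makes stopping for effect depend on crossing "the Lan DeMets group sequential monitoring boundary corresponding to a P-value for effect of less than 0.005", a value it marks as approximate. The charter (Appendix 4) and the SAP section on interim analyses name the O'Brien-Fleming alpha-spending function. On a crossing, the charter says that the committee will recommend pausing or stopping, and the SAP says that it may. Stopping for futility is excluded. The recommendation does not bind: "The DMSC will be advisory to the MC", and the Management Committee decides.

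**Final analysis.** Protocol 10.2.1 uses intervals "using 95% CIs for the analyses of primary outcome (P-value 0.05". The SAP reports results "with 95% CIs for the primary analysis of the primary outcome (analysis 1) (P-value <0.05". The changes listed for March 2022 still refer to 95% intervals. Adjusted significance levels are mentioned only for the interim analyses.

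**The concern.** A spending function divides one total alpha over all looks. Whatever is spent at 50% is no longer available at the end. A plan that spends some alpha at the interim and then tests at the full 0.05 has two chances to claim an effect, which together exceed 5%. The final 95% interval is also slightly too narrow for a two-look design.

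At stake are the stated 5% for the primary outcome and the reading of a result close to the threshold. No futility stop exists to offset the excess.

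**Working it through.** **1. The plan's own figure.** Inputs from Protocol 10.1.1: 45% control mortality, 7 points absolute reduction (38%), alpha 0.05 two-sided, power 80%. With mean rate 0.415,

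n = [1.960·√(2·0.415·0.585) + 0.8416·√(0.45·0.55 + 0.38·0.62)]² / 0.07² = 776.6, so 777 per arm and 1554 in total.

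This reproduces the stated size. It is the fixed-sample formula at 0.05, with no allowance for an interim test.

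**2. The interim boundary.** The information fraction is t = 777/1554 = 0.5. The documents do not say which convention applies, so I take four:

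- O'Brien-Fleming spending, 0.025 per side: 4·[1 − Φ(2.2414/√0.5)] = 0.00305, z = 2.963.
- The protocol's approximate value: 0.005, z = 2.807.
- Classic two-look O'Brien-Fleming: 0.00517, z = 2.797.
- Spending 0.05 directly: 2·[1 − Φ(1.960/√0.5)] = 0.00557, z = 2.772.

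**3. Overall error with the final test at 0.05.** Under the null, Z₁ (interim) and Z₂ (final) are bivariate normal with correlation √0.5 = 0.707. A crossing is taken to stop the trial and count as an effect:

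error = 1 − P(|Z₁| < c₁ and |Z₂| < 1.960).

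The final level that holds 5% replaces 1.960 by the c₂ for which this equals 0.05.

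| Interim P | c₁ | Overall error | c₂ | Final level | Interval |
|---|---|---|---|---|---|
| 0.0031 | 2.963 | 5.10% | 1.9686 | 0.0490 | 95.1% |
| 0.005 | 2.807 | 5.19% | 1.9767 | 0.0481 | 95.2% |
| 0.0052 | 2.797 | 5.20% | 1.9774 | 0.0480 | 95.2% |
| 0.0056 | 2.772 | 5.22% | 1.9793 | 0.0478 | 95.2% |

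A simulation of 20 million draws gave 5.10%, 5.19% and 5.22% for the first, second and fourth rows. In one direction, the chance of a false claim of benefit rises from 2.5% to between 2.55% and 2.61%.

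**4. If a stop must be confirmed.** The charter and the SAP let the committee recommend that the final decision to stop await an analysis of all participants included by then, judged again by the Lan-DeMets boundary. If both analyses must cross, and otherwise the trial runs to a final test at 1.960,

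error = 0.05 + P(both boundaries crossed and |Z_final| < 1.960).

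The second analysis is assumed to fall at 55% to 70% information. With per-side spending at both analyses the error is 5.06% to 5.04%. With 0.05 spent directly it is 5.12% to 5.08%. Reusing the first P-value boundary at 60% to 70% gives 5.01% to 5.07% across conventions.

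**5. Cost of adjusting.** Drift at the end is 0.07/√(2·0.415·0.585/777) = 2.800, and at the interim 2.800·√0.5 = 1.980. Two-look power, unadjusted against adjusted final level:

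- 0.0031: 80.06% against 79.82%, a loss of 0.24 points.
- 0.005: 80.13% against 79.67%, a loss of 0.46 points.
- 0.0056: 80.15% against 79.62%, a loss of 0.53 points.

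The standard error of the risk difference is √[(0.45·0.55 + 0.38·0.62)/777] = 2.493 points. The half-width goes from 1.960 × 2.493 = 4.89 points to 4.91 (1.9686) or 4.94 (1.9793), which is 0.4% to 1.0% wider.

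**The case against.** **The excess is tiny.** This stands. The plan states 5% without a decimal, and 5.10% to 5.22% rounds to it. On the per-side convention, the chance of continuing to the end and landing between 0.0490 and 0.0500 is 0.10% under the null and 0.24% under 45% against 38%.

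**The 5% is a sample-size input, and naming a spending function implies a reduced final level.** This stands in part. No section promises error control across looks to a decimal. But both documents print the final criterion as 0.05 with a 95% interval, and an analyst following them would use it.

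**The boundary is only advisory, and a stop may await a second analysis.** Both are true. They shrink the excess without removing it, unless the boundary is never acted on. A plan should not depend on its own stopping rule being ignored.

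**Two stronger readings are not supported.**

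- A reader might infer that Protocol 10.2.3 contradicts the charter, because per-side spending gives 0.0031 and not 0.005. But 10.2.3 gives an upper value and calls it approximate: 0.0031 lies below it, and 0.0052 and 0.0056 are close to it. What is missing is the convention.
- A reader might infer a larger inflation from the charter's "The DMSC can, at any time during the trial, request the distribution of events, including outcome measures". That is a right to see data. No further mortality test is scheduled and no information fraction is given for one, so any figure for it would rest on the reader's own assumptions.

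**Conclusion.** The point holds and is minor. The final level was not lowered for the alpha spent at the 50% mortality look. Overall two-sided type 1 error is 5.10% to 5.22%, and 5.19% at the protocol's own 0.005. This assumes one mortality look at exactly half the information, a crossing that leads to stopping and a claim of effect, and a final test at 0.05.

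Under a confirmation requirement the error is about 5.04% to 5.06% with per-side spending, and on other readings between 5.01% and 5.12%. If the boundary is never acted on, it is 5.0%.

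Only a final P between about 0.048 and 0.050 would be read differently. Nothing here puts the trial's size in doubt or makes the 95% interval materially misleading.

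**What to change.** In Protocol 10.2.1 and the SAP section on the primary outcome, state that the final two-sided level is what remains of 0.05 after the alpha spent at the mortality look or looks, under the boundary convention actually used at the third interim and at the actual information fraction, with an interval of matching coverage. For one look at exactly 50%:

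- interim boundary P<0.0031: final level 0.0490, 95.1% interval;
- interim boundary 0.005: 0.0481, 95.2% interval;
- interim boundary 0.0056: 0.0478, 95.2% interval.

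In Protocol 10.2.3 and the charter, record which convention was used. Do not write in a new interim boundary after the fact: that would rewrite a past rule, and a final level of 0.0490 would not hold 5% if the interim was judged at 0.005.

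The SAP's list of changes dates the final analyses to March 2022. The adjusted level and interval should therefore appear beside the reported 95% interval, labelled as added after those analyses.

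The cost is 0.24 to 0.53 points of power and an interval 0.4% to 1.0% wider. No new data and no change of conduct are needed.
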